#### 5.4 Discontinue treatment (remove patient from study), for following:

- 1) AST or ALT >5 times ULN (grade 3) or total bilirubin >3 times ULN (grade 3) or severe/life-threatening immune-mediated hepatitis: **Permanently discontinue.**
- 2) Colitis
  - I. Colitis: (grade 4); also administer high-dose systemic corticosteroids (prednisone 1 to 2 mg/kg daily or equivalent) followed by a corticosteroid taper
  - II. Colitis (recurrent)
- 3) Pneumonitis  
Pneumonitis (grade 3 or 4); also administer high-dose systemic corticosteroids (prednisone 1 to 2 mg/kg daily or equivalent) followed by a corticosteroid taper
- 4) Inability to reduce corticosteroid dose to prednisone  $\leq$ 10 mg/day (or equivalent) within 12 weeks.
- 5) Other adverse reactions that are life-threatening, severe or grade 3 treatment related adverse reactions that recur, or persistent grade 3 treatment-related toxicity that does not recover to grade 1 or resolve within 12 weeks (except alopecia)..
- 6) Creatinine >6 times ULN (grade 4): Permanently discontinue; initiate high-dose systemic corticosteroids
- 7) Severe (grade 3) or life-threatening (grade 4) transaminase elevations: Permanently discontinue treatment and initiate high-dose systemic corticosteroids (prednisone 1 to 2 mg/kg daily or equivalent)

#### 5.5 Hepatic Impairment

##### *Hepatic impairment prior to treatment initiation:*

Mild impairment (total bilirubin  $\leq$  ULN and AST > ULN or total bilirubin <1 to 1.5 times ULN and any AST): No dosage adjustment necessary.

Moderate (total bilirubin >1.5 to 3 times ULN and any AST) to severe (total bilirubin >3 times ULN and any AST) impairment: There are no dosage adjustments provided in the manufacturer's labeling (has not been studied).

##### *Hepatotoxicity during treatment:*

AST or ALT >3 to 5 times ULN or total bilirubin >1.5 to 3 times ULN: Withhold treatment; may resume therapy upon recovery to grade 0 or 1 toxicity (AST/ALT grade 1 is >ULN-3xULN, Total bilirubin grade 1 is >ULN-1.5xULN) .

AST or ALT >5 times ULN or total bilirubin >3 times ULN or severe/life-threatening immune-mediated hepatitis: Permanently discontinue.

Immune-mediated hepatitis:

Grade 2 or higher transaminase elevations (with or without total bilirubin elevations): Withhold treatment and initiate high-dose systemic corticosteroids (prednisone 1 to 2 mg/kg daily or equivalent)

Severe (grade 3) or life-threatening (grade 4) transaminase elevations: Permanently discontinue

treatment and initiate high-dose systemic corticosteroids (prednisone 1 to 2 mg/kg daily or equivalent)

## **5.6 Thyroid Disorders**

Thyroid disorder (hyperthyroidism or hypothyroidism): There are no recommended dosage modifications.

## **5.7 Treatment of Nivolumab Related Infusion Reactions**

Since nivolumab contains only human immunoglobulin protein sequences, it is unlikely to be immunogenic and induce infusion or hypersensitivity reactions. However, if such a reaction were to occur, it might manifest with fever, chills, rigors, headache, rash, pruritus, arthralgias, hypo- or hypertension, bronchospasm, or other symptoms. All Grade 3 or 4 infusion reactions should be reported within 24 hours to BrUOG and reported as an SAE if it meets the criteria. Infusion reactions should be graded according to NCI CTCAE (version 4) guidelines.

Treatment recommendations are provided below and may be modified based on local treatment standards and guidelines as appropriate:

**For Grade 1 symptoms** (mild reaction, infusion interruption not indicated, intervention not indicated): Remain at bedside and monitor subject until recovery from symptoms. The following prophylactic premedications are recommended for future infusions: diphenhydramine 50 mg (or equivalent) and/or paracetamol 325 to 1000 mg (acetaminophen) at least 30 minutes before additional nivolumab administrations.

**For Grade 2 symptoms** (moderate reaction requires therapy or infusion interruption but respond promptly to symptomatic treatment [eg, antihistamines, non-steroidal anti-inflammatory drugs, narcotics, corticosteroids, bronchodilators, IV fluids], prophylactic medications indicated for < 24 hours) Stop the nivolumab infusion, begin an IV infusion of normal saline, and treat the subject with diphenhydramine 50 mg IV (or equivalent) and/or paracetamol 325 to 1000 mg (acetaminophen); remain at bedside and monitor subject until resolution of symptoms. Corticosteroid or bronchodilator therapy may also be administered as appropriate. If the infusion is interrupted, then restart the infusion at 50% of the original infusion rate when symptoms resolve; if no further complications ensue after 30 minutes, the rate may be increased to 100% of the original infusion rate. Monitor subject closely. If symptoms recur then no further nivolumab will be administered at that visit. Administer diphenhydramine 50 mg IV and remain at bedside and monitor the subject until resolution of symptoms. The amount of study drug infused must be recorded on the appropriate page. The following prophylactic medications are recommended for future infusions: diphenhydramine 50 mg (or equivalent) and/or paracetamol 325 to 1000 mg (acetaminophen) should be administered at least 30 minutes before additional nivolumab administration. If necessary, corticosteroids (recommended dose: up to 25 mg of IV hydrocortisone or equivalent) may be used.

**Grade 3 or 4 symptoms** (severe reaction, Grade 3 prolonged [ie not rapidly responsive to symptomatic medication and/or brief interruption of infusion]; recurrence of symptoms following initial improvement; hospitalization indicated for other clinical sequelae [eg, renal impairment, pulmonary infiltrates]). Grade 4: (life-threatening, pressor or ventilatory support indicated): Immediately discontinue infusion of nivolumab. Begin an IV infusion of normal saline and treat the subject as follows: recommend bronchodilators, epinephrine 0.2 to 1 mg of a 1:1,000 solution for subcutaneous administration or 0.1 to 0.25 mg of a 1:10,000 solution injected slowly for IV

administration, and/or diphenhydramine 50 mg IV with methylprednisolone 100 mg IV (or equivalent) as needed. Subjects should be monitored until the investigator is comfortable that the symptoms will not recur. **Nivolumab will be permanently discontinued.**

Investigators should follow their institutional guidelines for the treatment of anaphylaxis. Remain at bedside and monitor subjects until recovery from symptoms. In case of late-occurring hypersensitivity symptoms (eg, appearance of a localized or generalized pruritus within 1 week after treatment), symptomatic treatment may be given (eg, oral antihistamine or corticosteroids).

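### Protocol section 5.7 gives incompatible instructions on later nivolumab dosing when a grade 2 infusion reaction recurs after the infusion is restarted

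*Protocol*

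**What the plan says.** Protocol section 5.7 sets out the handling of nivolumab infusion reactions by grade.

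- **Grade 2.** The infusion is stopped and symptoms are treated. Then: "If the infusion is interrupted, then restart the infusion at 50% of the original infusion rate when symptoms resolve". For a recurrence: "If symptoms recur then no further nivolumab will be administered at that visit". The paragraph goes on to later dosing: "The following prophylactic medications are recommended for future infusions".
- **Grade 3 or 4.** The parenthesis that describes these reactions includes "recurrence of symptoms following initial improvement" among several features separated by semicolons. The paragraph closes, in bold: "Nivolumab will be permanently discontinued".
- **Reporting.** The opening of 5.7 says: "All Grade 3 or 4 infusion reactions should be reported within 24 hours to BrUOG and reported as an SAE if it meets the criteria". The grade 2 paragraph has no corresponding reporting instruction.
- **Grading.** "Infusion reactions should be graded according to NCI CTCAE (version 4) guidelines". The appendix on toxicity criteria says only where CTCAE version 4 can be obtained.
- **Flexibility.** The opening of 5.7 also allows the treatment recommendations to be adapted to local standards.

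Elsewhere, section 5.4 item 5 covers discontinuation for severe or grade 3 treatment-related reactions that recur. Section 11.5 asks for telephone notice of any SAE within 24 hours.

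**The concern.** Two sites could each follow section 5.7 as written and handle the same event differently. One would end the infusion for the day and expect to give nivolumab again at the next cycle with premedication. The other would withdraw the drug for good. At stake is whether a patient who has reacted twice in one visit is exposed again, so the protocol should give one answer.

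There is also a reporting consequence. If the event is taken as grade 2, section 5.7 does not ask for a 24-hour report. If it is taken as grade 3, it does. For events that are not serious, the coordinating office might hear promptly of one patient and not of another with the same course.

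**Working it through.** The documents state no figure on this point, so the check is a comparison of texts. Take one patient: a grade 2 reaction, infusion stopped, symptoms resolve, infusion restarted at half rate, symptoms return.

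1. *Does the patient meet the grade 2 recurrence sentence?* Yes. It is written for this sequence.
2. *Does the patient also meet the grade 3 descriptor?* As worded, yes. The restart is conditional on resolution, so any return of symptoms after it comes after an improvement. The overlap therefore covers every patient who reaches the grade 2 recurrence sentence by way of a restart.
3. *What follows under each paragraph?*

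| | Grade 2 paragraph | Grade 3 or 4 paragraph |
|---|---|---|
| Infusion that day | Stopped for that visit | Stopped |
| Later nivolumab | Premedication recommended for later infusions, which presupposes that they occur | Permanently discontinued |
| Acute treatment | Saline, diphenhydramine; steroid or bronchodilator if appropriate | Saline, diphenhydramine with methylprednisolone, bronchodilators, epinephrine, as needed |
| 24-hour report under 5.7 | Not asked for | Asked for |

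Only the row on later nivolumab holds incompatible outcomes. Acute treatment differs in intensity, and reporting differs because it is tied to grade.

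4. *Does another part of the protocol break the tie?*
   - Sections 5.1 to 5.4 do not name infusion reactions.
   - Section 5.4 item 5 applies to a reaction already classed as severe or grade 3. It does not say whether a grade 2 reaction that recurs on restart moves into that class.
   - The CTCAE reference names an external grading standard. Section 5.7 has no rule of its own for re-grading a reaction that returns after restart, and it gives no order of precedence between its printed descriptors.
   - The local-modification clause gives latitude but does not say which paragraph is the starting point.
   - The paragraph that closes 5.7 deals with anaphylaxis and late-occurring symptoms.
   - Section 12 lets the physician stop treatment on judgement. That does not assign a grade or trigger a report.

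5. *How far does the reporting gap reach?* A recurrence that meets the SAE definition needs 24-hour telephone notice under section 11.5 whichever paragraph is used. The uncertainty is confined to events that are not serious.

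**The case against.** The case on the other side has several parts.

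- **The grade 3 or 4 parenthesis opens by describing a severe reaction.** Its other features could be read as qualifying severe reactions only, which would leave a mild recurrence in the grade 2 paragraph. That reading is possible. But the semicolons set recurrence apart with no severity condition attached, so careful readers can differ on whether the drug stops for good.
- **The grade 2 wording limits that day's infusion and does not order later dosing to resume.** This is right. The premedication sentence is also written for grade 2 patients in general, including those who never recur. Continuation is therefore the natural inference and not an explicit command. Even so, a paragraph that plans for later infusions cannot be squared with permanent discontinuation.
- **Grade is assigned by CTCAE version 4, and the path follows from grade.** This carries some weight. CTCAE is not among the documents, so whether it would settle the grade cannot be checked here. If it did, the printed paragraphs would still need to agree with it, because staff at the bedside will work from them.
- **Local modification is allowed.** This softens any complaint that sites differ in acute treatment. It does not settle the grade, and the discontinuation sentence is worded as mandatory.

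A reader might go further and infer that the paragraphs are opposed on acute treatment and reporting as well. They are not. Both stop the infusion, give saline and use diphenhydramine, and serious events are notified within 24 hours under either.

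A reader might also try to express the conflict as an effect on the trial result: one patient is 1/18 = 5.6% of stage 1, and two years of two-weekly dosing is 104/2 = 52 infusions. The first is the weight of any stage 1 patient. The second assumes treatment for the full two years. Neither shows that the choice of paragraph changes a response. Patients removed for toxicity without progression continue CT follow-up under the study calendar, so their response can still be observed.

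**Conclusion.** The conflict stands for later dosing: a grade 2 reaction that resolves, is restarted and recurs fits two paragraphs of section 5.7 that cannot both be followed. A secondary ambiguity stands for the 24-hour report of non-serious events. Both rest on reading the recurrence descriptor as printed, without an implied severity condition, and on the documents containing no rule of precedence.

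The size cannot be given as a rate, because the documents report no frequency of recurrence. Section 5.7 itself regards infusion reactions as unlikely, so few patients should be affected. The importance lies in the safety of those few and in consistent handling across sites. The documents do not support a claim that the response rate is biased. The Simon design (18 then 33 patients, 20% against 40%) is unaffected. No view is taken on which clinical rule is right.

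**What to change.** Reconcile the grade 2 and grade 3 or 4 paragraphs of section 5.7 so that recurrence after a restarted infusion appears under one grade only, with one instruction on later dosing and one reporting rule. The wording should be checked against CTCAE version 4, since section 5.7 names it as the grading standard. Section 5.4, which does not name infusion reactions, should be aligned with the result. The sponsor's clinical lead decides which rule applies.

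The cost is a short protocol amendment with its usual review. It needs no new data, no new procedures, and no change to the sample size or analysis.

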#### 6.0 SCHEDULE OF EVALUATIONS / STUDY CALENDAR

Parameter	Pre-study (to be sent to BrUOG prior to registration)	Within 3 days prior to Day 1 of Each Cycle of Nivolumab (approximately every 2 weeks) F	While on Nivolumab therapy (Every 12 weeks approximately every 6 cycles)	Ablation L Cycles 1(1 week after starting drug) and prior to each additional ablation (if performed)	End of Treatment (2 week window provided)	30 days post last dose of drug	FU D
Informed Consent (within 30 days of day 1) *pts are to be re-consented if ICF will be outside 30 day window	X						
Demographics	X						
Conmed log P	X	X	X	X	X		
Nivolumab K		X					
Optional labs: 3, 6ml purple top tubes to [name] at RIH at multiple time points	X	X O		X O			X O
Optional Tissue biopsy				X M			
History G	X			X			
Physical examination	X	X Q			X	X I	
Weight	X	X					
Vital signs	X	X					
Toxicity Assessment	X	X			X	X H	
Performance Status	X	X			X		
CBC, diff, platelet count	X (within 14 days)	X			X		
Na, K, BUN, Cr, AST, ALT, Bili	X (within 14 days)	X			X		
Ca, Mg, PO4	X (within 14 days)	X			X		
INR, TSH	X (within 14 days)						
Pre-Ablation labs: PLT, PT, PTT, INR				(within 2 weeks of ablation up to day of (prior to) N			

Serum Pregnancy E	X (within 7 days of drug)						
CT scan of Chest/abd/pelvis	X AC (with in 6 weeks)		X CJ		X CJ (CT does not need to be repeated if done in prior 2 months)		X D
CT scan or MRI of brain	X(within 6 weeks)		X (only if clinically indicated)		X (only if clinically indicated)		X
EKG B	X						
Survival and Disease status						X	X D

A- CT Scan for disease assessment to be performed within 6 weeks of study entry. Report required. (chest X-ray okay with baseline).

B- EKG within 8 weeks of study entry. Report required

C- An MRI or PET scan may substitute for disease assessment.

D- For patients who are removed from protocol treatment due to toxicity, without progression, Follow-up until disease progression will include CT, disease free and overall survival every 3 months (a month window is allotted for scheduling). CT scans may be done outside of the 3 month window as per MD discretion; however it is suggested that CT scans be done q 3 months. For patients who come off study for progression, overall survival is to be reported every 3 months (a month window is provided). Follow-up will be for 5 years.

E post-menopausal women (surgical menopause or lack of menses  $\geq 12$  months) do not need to have a pregnancy test, document status. If HCG is not drawn, sites are asked to document menopausal status on lab form.

F It is appropriate to use labs from screening for cycle 1 day 1, if labs are within 14 days (pregnancy must be within 7 days as noted above for applicable patients). A physical exam within 7 days prior to cycle 1 day 1 may be utilized. PS, weight, vitals, conmeds, and AE assessment can be used from screening for cycle 1 if assessments are within 14 days of treatment. Labs and physical exam for all subsequent cycles can be within 3 days prior to day 1 of treatment. Another day is provided for holidays.

G Physician note required to be sent. For ablation time points, sites are to submit consult notes from appointment pre-ablation and if consult occurs post ablation that not is also to be sent.

H Adverse event evaluation, inclusive of SAE evaluation, will be done 30 days post last dose of drug (+1 week window). SAEs occurring outside this 30 day window must be reported if the event is considered to be possibly related to the drug, even if patient begins a new treatment. If a patient begins a new treatment, AE evaluation will be stopped unless the patient experiences an event that is thought to be possibly related to the study treatment. It is required to inform BrUOG of patient beginning a new treatment.

I Physical to be done in coordination with 30 day toxicity assessment (+ 1 week allowed). Physical post 30 day assessments not required per study

JCT scans (or disease assessment by MRI or PET) to be completed approximately every 12 weeks (approximately every 6 cycles). For patients staying on study post initial PD – see section 7.3- next scan to confirm PD to be done in 1 month time period if patient remains on study.

K: Cycles are 14 days (+/- 3 days) however, it will not be considered a deviation if a cycle or pre-cycle assessment must be adjusted to accommodate scheduling or holidays. Adjustment must be documented with reason to BrUOG. Cycles not to be < 10 days.

L: Sites must submit the procedure report and the imaging report from each ablation procedure to BrUOG and document response. The first ablation should be performed within 1 week (7 days) of the initial treatment with nivolumab to occur within the first cycle (14 days) of treatment. Additional ablations may be performed as per institutional standard of care. There must be a minimum of 60days between each ablation (preference is 60-90 days). This means that the first ablation will occur in cycle 1 (post receiving approximately 1 week of drug) and the sixth cycle

M: During the same procedural period as ablation, a tumor tissue biopsy may be obtained prior to each ablation for future correlative studies such as assessment of PD-L1 by immunohistochemical staining.

N: Pre-ablation labs to be done within 2 weeks of ablation (prior to). If the counts are done early and would preclude the patient from ablation, labs should be repeated on the day of the procedure prior to cancelling.

O. Optional labs: If patient agrees to optional labs; 3, 6ml purple tops will be taken before and after ablation and then post treatment. First set to be taken at baseline pre-nivolumab, second set to be taken cycle 1 pre-ablation and post Nivolumab

dosing. Third set to be taken post ablation with the pre cycle 2 nivolumab blood work. Fourth set of tubes to be taken approximately 3 months post first ablation and then fifth set to be taken approximately 3 months later, approximately 6 months after first ablation. If patient undergoes a second ablation, one set (3 purple tops) will be taken prior to ablation and one set will be taken post ablation.

P- Conmeds to be collected at baseline and then each cycle. Conmeds to also include documentation of administration of agents/drugs/topicals etc for toxicity management. Final conmed log to be sent with off study (end of treatment) materials.

Q- Physical and visit with treating MD is not required prior to each cycle dosing but may be done. It is required that the physical and visit with MD occur every other cycle however (i.e. cycle 1 (if PE not within time frames allowed from screening visit), 3, 5, 7 etc and at end of study treatment and 30 days.) All other pre-dosing assessments are required prior to each cycle.

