## **7.0 RESPONSE ASSESSMENT:**

**7.1. Objective Response Rate by RECIST:** Response Evaluation Criteria in Solid Tumors (RECIST), version 1.1 will be used to assess responses by CT/ MRI but response criteria are modified by the immune-related response criteria as described in section 7.3. The first scheduled assessment of tumor response will be performed approximately 12 weeks after the first dose of nivolumab and approximately every 12 weeks thereafter. Patients in whom a scheduled scan showed initial disease progression will be allowed to continue receiving treatment until a confirmatory scan was obtained at least 1 month later. (see section 7.3)

Use of RECIST to clinically assess response for patients who progress with sum of target lesion is > 20 % then should use IrRC (if patient is asymptomatic, no vital organ involved etc.)

**7.2.** Overall responses derived from investigator reported data, with assessment according to immune-related response criteria.

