#### **7.4 Modified immune-related response criteria (irRC), derived from RECIST 1.1**

This new classification is based on the recent learning from clinical studies with cancer immunotherapies that even if some new lesions appear at the beginning of a treatment or if the total tumor burden does not increase substantially, tumor regressions or stabilizations might still occur later. The irRC were created using bidimensional measurements (as previously widely used in the World Health Organization criteria). For this trial, the concepts of the irRC are combined with RECIST 1.1 to come up with the modified irRC.

For modified irRC, only target and measurable lesions are taken into account. In contrast to the RECIST 1.1 criteria, the modified irRC criteria (a) require confirmation of both progression and response by imaging at 12 weeks after initial imaging and (b) do not necessarily score the appearance of new lesions as progressive disease if the sum of lesion diameters of target lesions (minimum of 10 mm per lesion, maximum of 5 target lesions, maximum of 2 per organ) and measurable new lesions does not increase by  $\geq 20\%$ .

The same method of assessment and the same technique should be used to characterize each identified and reported target lesion(s) at baseline, during the trial, and at the end of trial visit. All measurements should be recorded in metric notation. The modified irRC based on RECIST 1.1 are displayed below.

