**Overall Responses Derived from Changes in Index, Non-Index, and New Lesions**

Measurable Response	Non-Measurable Response		Overall Response Using Modified irRC
Index and New, Measurable Lesions	Non-Index Lesions	New, Non-Measurable Lesions	
Decrease 100%	Absent	Absent	irCR 
Decrease 100%	Stable	Any	irPR 
Decrease 100%	Unequivocal progression	Any	irPR 
Decrease $\geq 30\%$	Absent / Stable	Any	irPR 
Decrease $\geq 30\%$	Unequivocal progression	Any	irPR 
Decrease $< 30\%$ to increase $< 20\%$	Absent / Stable	Any	irSD
Decrease $< 30\%$ to increase $< 20\%$	Unequivocal progression	Any	irSD
Increase $\geq 20\%$	Any	Any	irPD

 Decreases assessed relative to baseline

 Assuming that the response (irCR and irPR) and progression (irPD) are confirmed by a second, consecutive assessment at least 4 weeks apart (normally it should be done 6 weeks apart).

Post Ablation changes observed on radiographic studies that are larger in size than preablation masses will not be considered tumor progression if no enhancement within the lesion that suggests tumor growth.

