**Inclusion Criteria**

- \_\_\_\_\_ (y/n) Pathologically or cytologically confirmed NSCLC
- \_\_\_\_\_ (y/n) Stage IIIB or stage IV.
- \_\_\_\_\_ (y/n) Progression after at least 1 line of systemic treatment (IV or oral) for metastatic or locally advanced disease. Patients progressing within 6 months of completion of neoadjuvant or adjuvant chemotherapy are also eligible. Radiation does not count as 1 line.
- OR
- \_\_\_\_\_ (y/n) Patients progressing within 6 months of completion of neoadjuvant or adjuvant chemotherapy are also eligible without having treatment for metastatic disease (for example patient with stage I disease undergoes resection, receives systemic chemotherapy and then progresses to the liver (now stage IV) within 6 months of chemotherapy). Radiation does not count as 1 line.
- \_\_\_\_\_ (y/n) At least 1 site of measurable disease that will not be treated with ablation
- \_\_\_\_\_ (y/n) Ablation for advanced lung cancer is being considered by the treating physician for treatment or prevention of symptoms such as pain, bleeding or obstruction. Documentation to be sent in writing from MD to confirm criterion.
- \_\_\_\_\_ (y/n) At least 3 weeks since prior systemic treatment and/or radiation therapy for patient's NSCLC (from treatment day 1 on study)
- \_\_\_\_\_ (y/n) No brain metastases except for patients whose metastases have been removed by surgical resection or have had stereotactic radiation or gamma knife with no evidence of active disease on MRI within 28 days of starting treatment.
- \_\_\_\_\_ (y/n) Voluntary, signed written informed consent, Date signed \_\_\_\_\_
- \_\_\_\_\_ (y/n) Age  $\geq 18$
- \_\_\_\_\_ (y/n) ECOG PS 0-2
- \_\_\_\_\_ (y/n) Life expectancy  $\geq 12$  weeks (must be confirmed by treating MD in writing)
- \_\_\_\_\_ (y/n) Must be willing to consent to use effective contraception while on treatment and for at least 2 months afterwards.
- \_\_\_\_\_ (y/n) CT scan of the chest/abdomen/pelvis within 6 weeks of study entry. Patients can have PET/MRI of the chest/abdomen instead. Chest Xray okay.
- \_\_\_\_\_ (y/n) EKG within 8 weeks study entry
- \_\_\_\_\_ (y/n) Absolute neutrophil count  $\geq 1,000/\text{ul}$ , Date \_\_\_\_\_
- \_\_\_\_\_ (y/n) Platelet  $\geq 75,000/\text{uL}$ , Date \_\_\_\_\_
- \_\_\_\_\_ (y/n) Total bilirubin  $\leq 1.5 \times \text{ULN}$ , Date \_\_\_\_\_
- \_\_\_\_\_ (y/n) AST  $\leq 3 \times \text{ULN}$
- \_\_\_\_\_ (y/n) Creatinine  $\leq 1.5 \text{ mg/dl}$  or creatinine

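### The calendar lets PET replace CT, and accepts chest X-ray at baseline, while response is defined on CT/MRI diameters measured by one method throughout

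*Protocol*

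**What the plan says.** The Protocol speaks to imaging in three places.

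- **Study calendar, section 6.0.** The default is CT of chest, abdomen and pelvis. Footnote C, attached to the baseline, on-treatment and end-of-treatment cells, reads "An MRI or PET scan may substitute for disease assessment". Footnote J repeats the option for the on-treatment and end-of-treatment scans: "CT scans (or disease assessment by MRI or PET) to be completed approximately every 12 weeks". Footnote A adds "chest X-ray okay with baseline". The follow-up cell carries footnote D, which names CT.
- **Appendix B checklist.** After the CT requirement it says "Patients can have PET/MRI of the chest/abdomen instead. Chest Xray okay".
- **Section 7.** In 7.1, RECIST 1.1 "will be used to assess responses by CT/ MRI"; PET is not named. In 7.4, partial response is a fall of at least 30% in the sum of longest diameters, and a target lesion must measure at least 10 mm. The same section has a consistency rule ("The same method of assessment and the same technique should be used to characterize each identified and reported target lesion(s") covering baseline, the trial period and the end-of-trial visit. The note under the 7.4 response table says that a mass larger after ablation "will not be considered tumor progression if no enhancement within the lesion that suggests tumor growth".

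No section requires contrast. The SAP repeats the design paragraph and says nothing on imaging.

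**The concern.** The primary endpoint is response rate, and response is a percentage change between two diameter sums. That requires diameters at both times, obtained in a comparable way over the same part of the body. The calendar is what a site follows when ordering scans, and it allows three departures: a PET with no stated measurable component, a baseline that may rest partly on chest X-ray, and a PET/MRI baseline that leaves out the pelvis. None is tied to the consistency rule in 7.4.

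A site could comply with section 6.0 and still supply an assessment that section 7 cannot score, or one compared with an unlike baseline. Errors could go either way. An unscorable patient may be lost as a responder, a change of method may look like shrinkage, and a lesion outside the baseline field may look like growth.

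A secondary gap is that the post-ablation rule depends on enhancement, while no scan has to be able to show it.

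**Working it through.** **1. What is permitted against what is needed**

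| Assessment | Calendar footnotes | Methods permitted | Needed by 7.1 and 7.4 |
|---|---|---|---|
| Baseline | A, C, and checklist | CT, MRI or PET; chest X-ray accepted; PET/MRI may cover chest and abdomen only | CT/MRI diameters |
| Every 12 weeks | C, J | CT, MRI or PET | CT/MRI diameters, same method as baseline |
| End of treatment | C, J | CT, MRI or PET | As above |
| Follow-up without progression | D | CT | No conflict in this footnote |

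The first three rows conflict. Sections 6.0 and 7.1 cannot both define the acceptable modality.

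**2. Coverage**

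Section 7.4 adds new measurable lesions to tumor burden. Let B be the baseline sum that was imaged and m the baseline diameter of a pelvic lesion that was not. Suppose every lesion shrinks by exactly 30%, the pelvic lesion is still measurable, and it would have been a target had it been imaged.

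- True change: (0.7B + 0.7m − B − m)/(B + m) = −30%, a partial response.
- Recorded change: (0.7B + 0.7m − B)/B = −30% + 70% × m/B.
- With m/B = 1/2: −30% + 35% = +5%, stable disease.
- With m/B = 5/7: −30% + 50% = +20%, the progression threshold when baseline is the nadir.

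The ratios are assumed. They show the mechanism, not how often it would occur.

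**3. The design that rests on this endpoint**

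Inputs from Protocol 17.1 and the SAP: 18 patients in stage 1, stop at 4 or fewer responses; 33 in total, reject at 11 or more; response rates 20% and 40%.

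P(reject | p) = Σ over x = 5 to 18 of P[Bin(18, p) = x] × P[Bin(15, p) ≥ 11 − x].

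- p = 0.20: 0.0458, within the stated 0.05.
- p = 0.40: 0.8011, matching the stated 80%.

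A search for the minimax design returns the same boundaries.

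**4. Sensitivity, with assumed rates**

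The documents give no rate of unscorable or mis-scored patients. Suppose a share u of patients has no scorable assessment and counts as non-responders. The effective rate at a true 40% is then 0.40 × (1 − u).

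| u | Effective rate | Power | Chance of stopping at stage 1 |
|---|---|---|---|
| 0 | 0.40 | 0.801 | 0.094 |
| 5% | 0.38 | 0.733 | 0.126 |
| 10% | 0.36 | 0.653 | 0.166 |
| 20% | 0.32 | 0.468 | 0.269 |

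Suppose instead that a share f of true non-responders is called responders through a change of method. The effective rate at a true 20% is then 0.20 + 0.80 × f.

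| f | Effective rate | Type I error |
|---|---|---|
| 0 | 0.200 | 0.046 |
| 1% | 0.208 | 0.059 |
| 2% | 0.216 | 0.074 |
| 5% | 0.240 | 0.134 |

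Power starts at 0.801, so the design has almost no reserve for measurement loss.

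**The case against.** The best defence is that section 7.4 already governs consistency. On that reading footnotes C and J list possible modalities and 7.4 forbids switching between them. This is partly right: the rule exists. But it says only that the same method should be used, the footnotes do not point to it, and it does not help a patient imaged by PET throughout if no diameters can be taken.

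PET may also mean PET with a CT good enough to measure. The documents do not say. If so, diameters are available and most of the problem goes, which is why the fix keeps that option.

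Section 7.4 further requires response to be confirmed by a second consecutive assessment, and up to five targets are summed, which dilutes an error in one lesion. Both points limit the damage from a single odd scan. Confirmation does not help when two successive scans are compared with the same unlike baseline.

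The pelvic problem needs a PET/MRI baseline without the pelvis and an unrecognised measurable lesion there, and a new lesion is not automatically progression under 7.4. It is a narrow route to error.

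Stronger readings are tempting but not supported:

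- A reader might infer that every patient's endpoint is exposed to the enhancement rule, because all are due an ablation in cycle 1. The rule is needed only when an ablated mass is larger than before, and it concerns progression. Section 3.1.5 keeps a non-ablated measurable site for tracking response.
- A reader might infer that a modality difference alone could create a response, for example 9 mm on a 30 mm lesion (30% × 30 mm). That is arithmetic only; the documents give no difference between modalities.
- A reader might infer that contrast CT should be mandatory, with MRI only as a fallback. Section 7.1 accepts CT or MRI without ranking them.

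**Conclusion.** The conflict is real and worth correcting. At baseline, every 12 weeks and at end of treatment, the calendar permits PET in place of CT with no condition on measurability or on the baseline method. At baseline it also accepts chest X-ray. Sections 7.1 and 7.4 need CT/MRI diameters by one method. The checklist's narrower PET/MRI coverage is a further inconsistency. The missing contrast requirement is secondary and bears mainly on progression calls in ablated lesions.

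The size cannot be fixed from the documents, because they do not say how often PET or chest X-ray would be used or whether PET includes a measurable CT. The sensitivity figures rest on assumed rates and treat errors as independent across patients. Footnote A does not say whether chest X-ray replaces the chest CT or accompanies it; the checklist wording reads more like a replacement.

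This is a fault in how the endpoint is measured. It does not make the stated sample size, type I error or power wrong.

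**What to change.** - Reword footnotes C and J along these lines: CT or MRI of chest, abdomen and pelvis, using the same modality, technique and coverage at baseline and at every response assessment (section 7.4). PET may be added, but substitutes only if it includes a diagnostic-quality CT used for the measurements.
- Remove chest X-ray as a substitute for baseline tumor measurement in footnote A and the checklist.
- Align the checklist's PET/MRI line with the calendar's chest, abdomen and pelvis.
- Under the 7.4 response table, state that when an enlarged ablated lesion is to be excused from progression, the scan used must be able to show enhancement.

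The cost is an amendment to footnotes, checklist and one note. CT is already the default, so probably only a few patients planned for PET alone or chest X-ray would need the protocol's standard CT or MRI instead. Sample size and decision boundaries stay as they are.
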